We also measured how much their symptoms bothered them and how their healthrelated QoL was affected by their condition using the QoL score questionnaire. The QoL score is a tool that measures how satisfied participants are with their health and well-being. We also asked participants to rate how much they improved and how satisfied they were with the treatment using validated tools. The results of our preliminary study were positive and showed that our new intervention was promising. This encouraged us to continue with our main trial and test our intervention further. We created and finalized the study protocol, which is the document that describes the details and procedures of our study. We developed all data collection tools and forms, which are the tools and documents that we use to collect and record data from participants. We obtained IRB approvals at the National Clinical Research Center for Child Health and Disease (Chongqing, China), which are approvals from a committee that oversees the ethical aspects of our study and protects the rights and welfare of participants. We offered standard training to all coordinators and interventionists, who are the people who help us run the study and deliver the intervention to participants. Our preliminary data helped us to determine how many participants we needed for our main trial.

The primary outcome in our study will be the change in median voiding frequency from enrollment to 4-week follow-up and 8-week follow-up. In our previous feasibility study, the mean number of voids per day was 16.0 (SD, 5.0) at enrollment. We used the power analysis program PASS 15.0 to estimate the sample size of this randomized controlled trial. A sample size of 87 participants per group was needed to detect a difference of 1.5 voids per day between groups at the 0.05 level of significance, achieving more than 95% power, assuming an estimated SD of 5.0 after 8 weeks of treatment. We plan to recruit 97 participants per group, anticipating a 10% follow-up attrition, to ensure adequate power for the trial, for a total of about 300 participants. Our sample size estimations are supported by our previous trial.

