9.5.1 Primary Outcome

The study aims to determine the primary outcomes of urinary frequency among three groups of participants. The frequency of urination will be recorded at three different points in time, i.e., when the participants enroll in the study, four weeks after starting the treatment, and eight weeks after starting the treatment. We will compare the frequency of urination between the groups at each time point, and assess changes in urination frequency from enrollment to four weeks after starting treatment. To record urinary frequency, we will use a bladder diary, and these outcomes will be considered continuous variables, with any positive integer value within a specified range.

To analyze the data, we will use the intention-to-treat approach to avoid bias from factors such as dropout or crossover. We will also handle missing data before analysis. Statistical tests will be applied to compare the groups based on data distribution and variance, which affects the reliability of results. For normally distributed data with homogeneous variance, we will use ANOVA, followed by post-hoc comparisons and Bonferroni correction to reduce Type I errors. We will report data changes using mean and SD and differences between groups using point estimation and 95% confidence intervals (95%CI).

For non-normally distributed data with heterogeneous variance, we will use the Kruskal-Wallis test to compare groups. Post-hoc comparisons between groups will be done using the Wilcoxon rank sum test, and p-values will be adjusted by Bonferroni correction. Data changes will be reported using median and IQRs, and differences between groups using the Hodges-Lehmann (HL) estimate of location shift and 95% confidence intervals (95%CI). P-values will also be adjusted for multiple comparisons to avoid false positives, and a two-tailed P-value less than .05 will be considered statistically significant.

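### Bonferroni adjustment of the three pairwise comparisons is valid but more conservative than three groups require; Holm or a closed test meets the same 5% limit with more power

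*Combined protocol and SAP*

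**What the plan says.** Section 9.5.1 chooses between two branches by distribution and variance. In the normal branch, "we will use ANOVA, followed by post-hoc comparisons and Bonferroni correction to reduce Type I errors". In the rank branch, a Kruskal-Wallis test is followed by pairwise tests: "Post-hoc comparisons between groups will be done using the Wilcoxon rank sum test, and p-values will be adjusted by Bonferroni correction". The threshold is that "a two-tailed P-value less than .05 will be considered statistically significant". Differences between groups are to be reported with 95% confidence intervals.

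Three things are not stated: whether the pairwise tests are run only if the omnibus test is significant, how many comparisons the Bonferroni correction divides by, and whether any adjustment covers the several time points at which the groups are compared.

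Section 9.1 (Specific Aim 1) states expectations that are all pairwise: VDS+SU better than SOL+SU, VDS+SU better than SU, and SOL+SU better than SU. Section 9.2 sizes the trial: "A sample size of 87 participants per group was needed to detect a difference of 1.5 voids per day between groups", "assuming an estimated SD of 5.0 after 8 weeks of treatment".

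**The concern.** The omnibus test answers none of the three questions in Aim 1; the pairwise tests do. Bonferroni tests every pair at one third of alpha. That is stricter than needed to hold family-wise error at 5% when there are only three groups, for two reasons.

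- **Holm** tests the smallest P at alpha/3, the next at alpha/2 and the last at alpha. It rejects everything Bonferroni rejects, sometimes more, and carries the same guarantee. It needs no omnibus test.
- **The closed test for three groups** rejects a pair only if both the omnibus P and the unadjusted pairwise P are below 0.05. If all three means are equal, the omnibus test protects. If exactly two are equal, only one true null hypothesis remains and its own 5% test protects.

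At stake is the chance of confirming the individual contrasts in Aim 1. That chance is already modest at the planned sample size.

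**Working it through.** **Inputs.** From section 9.2: 87 evaluable per arm, SD 5.0, difference 1.5 voids per day, alpha 0.05, 10% attrition. From section 9.5.1: two-sided testing. Three arms, so three pairs. Assumed: Bonferroni divisor 3, normal data with equal variance, one time point.

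**1. The plan's own figure.** One-way ANOVA F test, noncentrality λ = n Σ(μᵢ − μ̄)²/σ². With means 0/1.5/3:

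λ = 87 × (2.25 + 0 + 2.25)/25 = 15.66; critical F(2, 258) = 3.03; power = 95.05%.

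At n = 86 the power is 94.81%, so 87 is the smallest n that reaches 95%. Recruitment: 87/0.9 = 96.7, rounded up to 97. The plan's figure is therefore omnibus power under equal steps of 1.5. The spacing is inferred; it agrees with the ordering in Aim 1. With 1.5 as the largest difference, omnibus power is 51.7% (0/0/1.5) or 40.3% (0/0.75/1.5).

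**2. One pair, 1.5 voids apart.** Two-sample t test, noncentrality 1.5/(5 × √(2/87)) = 1.979, 172 df:

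- alpha 0.05: critical t 1.974, power 50.3%
- alpha 0.05/3 = 0.0167: critical t 2.418, power 33.3%

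**3. Power by procedure.** Simulation with n = 87 and SD 5.0; Bonferroni and Holm without an omnibus condition.

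| True means | Contrast | Bonferroni | Holm | Closed test |
|---|---|---|---|---|
| 0/1.5/3 | each 1.5-void pair | 33% | 43% | 50% |
| 0/1.5/3 | the 3-void pair | 94% | 94% | 95% |
| 0/0/1.5 | each 1.5-void pair | 33% | 36% | 42% |
| 0/0.75/1.5 | the 1.5-void pair | 33% | 34% | 38% |

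Requiring a significant omnibus test before Bonferroni changes little: 33%, 33% and 32% for the 1.5-void pair in the three patterns.

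**4. Family-wise error over the three pairs, one time point.**

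| Procedure | All means equal | Two equal, third far away |
|---|---|---|
| Unadjusted, no omnibus condition | 12.2% | 5.0% |
| Bonferroni, no omnibus condition | 4.4% | 1.7% |
| Bonferroni after a significant omnibus test | 4.1% | 1.7% |
| Holm | 4.4% | 5.0% |
| Closed test | 5.0% | 5.0% |

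**5. Rank branch.** Kruskal-Wallis with Wilcoxon tests on the same normal data behaves alike. Under 0/1.5/3 the 1.5-void pair has about 32% power with Bonferroni and about 49% with the closed test. Error with all means equal is 4.4% and 5.0%.

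**6. Two time points.** If weeks 4 and 8 are each tested at 5% and were independent, the closed test would give 1 − 0.95² = 9.75%. Bonferroni over three pairs at each would give 1 − (1 − 0.044)² = 8.6%. Neither procedure controls error across visits.

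**The case against.** The strongest case for leaving the plan alone has five parts.

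- **No omnibus condition is written.** A reader might infer that Bonferroni sits on top of a significant omnibus test, so that the plan pays twice and gains nothing in error control. The documents do not support that. Section 9.5.1 sets no such condition, and as the text stands Bonferroni is itself the error control: it takes the family-wise rate from 12.2% to 4.4%. Even with a condition, actual error falls from 5.0% to 4.1% or 1.7%; what can be said is only that the 5% limit was already met. This stands in full. It does not remove the point, because Holm needs no omnibus condition and the closed test brings its own.
- **The size depends on the pattern of means.** A reader might take the fall from 50% to 33% as the general cost. It applies to 0/1.5/3 only. Where 1.5 is the largest difference, the closed test gains 5 to 9 points and Holm 1 to 3. The 3-void contrast barely moves. This stands.
- **Control is for one time point.** Swapping the method must not be presented as 5% control over weeks 4 and 8. This stands, and equally for Bonferroni.
- **Intervals.** Bonferroni has matching simultaneous intervals; Holm and the closed test do not. This is a real but small cost. The plan asks for 95% intervals without saying that they are simultaneous.
- **Rank branch conditions.** Section 9.5.1 reserves that branch for non-normal data with unequal variance, which the simulation did not cover. Holm relies only on valid pairwise P values, so this bears more on the closed test.

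It is also fair to say that sample size is the larger power problem. One 1.5-void pair has about 50% power before any correction; 95% would need 289 per arm unadjusted, or 363 at alpha/3.

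**Conclusion.** The Bonferroni adjustment in section 9.5.1 is valid and needlessly conservative. This is a cheap improvement, not an error in the plan. For a 1.5-void pair, power is about 33% as planned. Holm raises it to between 34% and 43% and the closed test to between 38% and 50%, depending on the true means; the upper figures belong to the pattern that reproduces the plan's 87 per arm. All three procedures keep family-wise error over the three pairs at or below 5% at a single time point.

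The figures rest on a divisor of 3, normal data with SD 5.0, 87 evaluable per arm and one visit. The change does not repair the low power of the pairwise tests at this sample size, and it does not address multiplicity across visits.

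**What to change.** In section 9.5.1, replace Bonferroni with Holm over the three pairs, in both the ANOVA and the rank branch. This requires no omnibus condition and can lose no rejection that Bonferroni would make. Alternatively, state that each pair's adjusted P is the larger of the omnibus P and the unadjusted pairwise P. That gives more power in the patterns examined, but relies on the omnibus test being valid for the data at hand.

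In either case, state the number of comparisons (three), and state that the control holds within one time point and does not cover weeks 4 and 8 together.

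The cost is a sentence or two in the SAP, settled before unblinding, with no extra participants or data. The downside is that simultaneous 95% intervals will not agree exactly with the Holm or closed-test decisions, so the SAP should say which kind of interval is reported. With the closed test, the ordinary 95% interval agrees with the decision whenever the omnibus test is significant.

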9.5.2 Secondary Outcomes

We will measure and compare secondary outcomes that are important for our study,

even though they are not the main outcomes. These outcomes comprise different types of variables, including continuous variables that are numerical and can take any value within a range. Some of the secondary outcomes that we will measure are the average change in urgency severity, the maximum change in urgency severity, the frequency of nocturia, the impact on the participants' QoL, and the severity of LUTS using the PLUTS score. We will measure these outcomes from the time participants enroll in the study to 4 and 8 weeks after they start the treatment. We will compare these outcomes and their changes over time between the groups.

To compare the groups, we will use various statistical tests based on how the data are distributed and how much they vary between the groups. The data's distribution describes how they are shaped and spread out and determines the statistical tests we can use. The variance of the data shows how much the values differ from each other within and between the groups, affecting the reliability of the results.

For normally distributed data with homogeneous variance, we will use the ANOVA test, which compares three or more groups with continuous data to identify significant differences between them. We will report the data and their change using mean and SD, which show the average and variability of the data, respectively. Additionally, we will perform post-hoc comparisons between groups to see which specific groups are different from each other. We will report these comparisons using point estimation and 95% confidence intervals (95%CI), which show how precise our

estimates are and how likely they are to include the true value. An adjusted P value will be reported for each comparison to avoid false positives.

For data that are not normally distributed or have heterogeneous variance, we will use the Kruskal-Wallis test to compare the groups. The Kruskal-Wallis test is suitable for comparing three or more groups with continuous data that do not meet the assumptions of ANOVA. We will report the data and their change using median and IQRs, which show the middle and range of the data. Additionally, we will perform posthoc comparisons between groups using the Wilcoxon rank-sum test, which can compare two groups with continuous data that do not meet ANOVA assumptions. We will report these comparisons using the HL estimate of location shift and 95% confidence intervals, which show how much one group differs from another group in terms of location or central tendency. We will also report an adjusted P value for each comparison.

We will assess and compare how participants perceive their improvement from enrollment in the study to 4 and 8 weeks after treatment initiation. This subjective outcome reflects how participants feel about their condition and treatment, which we will measure using a rating scale with categories such as much better, better, about the same, or worse. Since this is non-numerical, ordered categorical data, we will use the PP analysis set to analyze the subset of subjects who adhered to the protocol without major deviations. We will apply the Kruskal-Wallis test to compare groups based on their ratings of improvement at different time points, reporting the data using frequency and percentile. We will use a two-tailed P-value to determine statistical significance, setting a cutoff of less than .05, unless specified otherwise.

Additionally, we will record and compare participant satisfaction with the current treatment and their willingness to receive another therapy. This dichotomous outcome measures whether participants answered yes or no to whether they would like to receive another therapy. We will use the PP analysis set and the chi-square test to compare the groups based on their responses at different time points. We will report the data using frequency and percentile, and consider a P-value of less than .05 to be statistically significant, unless specified otherwise.

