This study is conducted in the form of a prospective, observer-blind, parallel-group randomized controlled clinical trial. The study population will consist of children aged five years or older diagnosed with OAB-dry at the Children's Hospital of Chongqing Medical University, with serum vitamin D levels below 35ng/ml. We will exclude patients with other systemic organic diseases and those with poor compliance, thus representing a relatively ideal cohort. Participants will be randomly assigned to one of three intervention groups, including a group receiving a combination of high-dose vitamin D and SU, a group receiving a combination of solifenacin and SU, and a group receiving SU alone.

This design allows for a thorough evaluation of the comparative efficacy and safety of various treatment regimens while minimizing sources of bias and confusion.

The randomized controlled design provides confidence that any observed differences between groups can be directly attributed to the experimental intervention, while the observer-blind method helps eliminate observer bias in assessment and outcome evaluation.

The parallel-group design facilitates direct comparisons between the three intervention groups, generating insightful information about the relative efficacy of each regimen. The combination of high-dose vitamin D and SU represents a novel therapeutic approach. The solifenacin and SU combination group is included to investigate the effects of previously described anticholinergics agents on outcomes. The control group receiving SU alone serves as an important reference point, providing a baseline for comparisons with other intervention measures.

4. SELECTION AND ENROLLMENT OF PARTICIPANTS.

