9. STATISTICAL CONSIDERATIONS

9.1 General Design Issues

Objective: The aim of this randomized controlled trial is to examine the effectiveness and safety of high-dose VDS plus SU for managing OAB-dry symptoms in pediatric patients with low vitamin D levels (<35ng/mL).

Specific Aim 1: The main outcome is the difference in post-treatment improvement between children who receive high-dose VDS plus SU and those who receive solifenacin plus SU or SU monotherapy for OAB-dry symptoms. The study expects that high-dose VDS plus SU will lead to more improvement than SU monotherapy and solifenacin plus SU. Furthermore, SU monotherapy will result in less improvement than solifenacin plus SU.

Specific Aim 2: The secondary outcome is the safety profile of high-dose VDS plus SU for OAB-dry symptoms in pediatric patients. The study anticipates that the safety profile of high-dose VDS plus SU will be similar to that of solifenacin plus SU or SU monotherapy at follow-up.

The study design is an 8-week randomized controlled trial, and all treatments will be administered in a group setting. Pediatric patients with OAB-dry symptoms will undergo 8 weekly sessions of high-dose VDS plus SU, solifenacin plus SU, or SU monotherapy. Independent assessors will evaluate the patients before the treatment, at mid-treatment (4-week follow-up), and at the 8-week follow-up to test the expectations. To account for attention, time, and group effects, all SU sessions will be administered in a group setting.

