9.5 Outcomes and data Analyses

We will employ diverse measures to describe the characteristics of our data, depending on their nature. For numerical data that are continuous and can take any value within a range, we will use the mean (the arithmetic average of all values), the SD (a measure of how much the values deviate from the mean), the median (the central value when the data are sorted from the lowest to the highest), and the interquartile ranges (IQRs) (the range containing the middle 50% of data). For non-numerical data that are categorical and can belong to multiple groups or categories, we will use the frequency (the number of occurrences for each category) and the percentile (the proportion of data that falls below a specific value or category).

We will examine our data for any outliers or missing values that could influence our analysis. Outliers refer to values that differ significantly from the majority of the data and may indicate errors or exceptional cases, while missing values are data points that are unavailable or not recorded. Although we will employ effective data collection and management practices, missing values may still occur due to various factors.

To estimate the missing values for continuous data, we will use multiple imputation. This approach replaces the missing values with plausible estimates based on the other available data. We will assume that the missing values are missing completely at random, meaning that their occurrence does not depend on any variable, including their value. We will also conduct a sensitivity analysis to determine if the missing values affect our results or conclusions.

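### The two categorical secondary outcomes get only a three-group test, with no pairwise comparison, effect estimate, interval or multiplicity adjustment, so a significant result would not show which groups differ

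*Combined protocol and SAP*

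**What the plan says.** The trial has three arms (section 3: "Participants will be randomly assigned to one of three intervention groups"). Aim 1 in section 9.1 is stated as contrasts between pairs of arms: "The study expects that high-dose VDS plus SU will lead to more improvement than SU monotherapy and solifenacin plus SU". It also expects SU alone to do worse than solifenacin plus SU.

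Section 9.5.2 covers two categorical outcomes, both in the per-protocol set:

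- **Perceived improvement**, an ordered rating at 4 and 8 weeks. The plan will "apply the Kruskal-Wallis test to compare groups based on their ratings of improvement at different time points, reporting the data using frequency and percentile", two-tailed at .05.
- **Willingness to receive another therapy.** "This dichotomous outcome measures whether participants answered yes or no to whether they would like to receive another therapy". For the analysis, "We will use the PP analysis set and the chi-square test to compare the groups based on their responses at different time points". Then: "We will report the data using frequency and percentile, and consider a P-value of less than .05 to be statistically significant".

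Neither paragraph names a pairwise test, an effect estimate, a confidence interval or an adjusted P value.

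The continuous outcomes are treated differently. Section 9.5.1 and the earlier paragraphs of 9.5.2 give them post-hoc comparisons, a point or Hodges-Lehmann estimate with 95% CI, and adjusted P values. Section 9.5.1 names Bonferroni as the adjustment.

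Section 9.5 explains the categorical summary as "the percentile (the proportion of data that falls below a specific value or category".

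**The concern.** A Kruskal-Wallis or chi-square test on three groups asks whether the groups are all alike. It does not say which pair differs, in which direction, or by how much. The questions of interest are VDS+SU against SU and VDS+SU against SOL+SU, so the planned test stops one step short.

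If the three-group test were significant, the authors would have to decide after seeing the data which contrast to report, on what scale, and whether to adjust it. If it were not significant, no interval would show what size of difference remained possible. The plan already avoids both problems for its continuous outcomes.

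There is also a smaller wording fault. The definition of 'percentile' in section 9.5 is not the percentage of children in a category, which is the summary these outcomes need.

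**Working it through.** **Inputs.** Three arms (section 3) and 87 evaluable children per arm (section 9.2). The plan gives no rates and no sample size for the categorical outcomes, so it has no figure of its own to reproduce here. The 87 comes from the primary outcome and fits the recruitment target: 87/(1 - 0.10) = 96.7, rounded up to 97. The per-protocol set could be smaller than 87 per arm. All counts below are assumptions.

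**Yes/no outcome.** Assume yes-counts of VDS+SU 35, SOL+SU 26 and SU 44 out of 87, that is 40.2%, 29.9% and 50.6%.

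*Three-group test.* Total yes = 105, so each arm has 35 expected yes and 52 expected no. The deviations are 0, -9 and +9.

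Chi-square = (0 + 81 + 81)/35 + (0 + 81 + 81)/52 = 4.63 + 3.12 = 7.74 on 2 df; P = 0.021.

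*Pairwise.* d = p1 - p2; SE = sqrt[p1(1 - p1)/87 + p2(1 - p2)/87]; 95% CI = d ± 1.96 SE.

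| Pair | d (points) | SE (points) | 95% CI | P | Bonferroni P (×3) |
|---|---|---|---|---|---|
| VDS+SU - SOL+SU | +10.3 | 7.2 | -3.8 to 24.4 | 0.15 | 0.46 |
| VDS+SU - SU | -10.3 | 7.5 | -25.1 to 4.4 | 0.17 | 0.51 |
| SOL+SU - SU | -20.7 | 7.3 | -34.9 to -6.4 | 0.005 | 0.016 |

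The plan would report P = 0.021. The only clear difference does not involve VDS+SU.

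**Similar three-group P, different message.** In order VDS+SU/SOL+SU/SU, counts of 26/26/44 give P = 0.005 and 26/44/44 give P = 0.006. VDS+SU minus SOL+SU is 0.0 points in the first and -20.7 points in the second.

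**Ordinal outcome.** Assume four categories from best to worst, with counts VDS+SU 22/33/22/10, SOL+SU 32/33/15/7 and SU 14/29/30/14. Kruskal-Wallis P = 0.0008. The probability of a better rating, counting ties as half, and the Wilcoxon P values are:

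| Pair | Probability of a better rating in the first arm | P | Bonferroni P |
|---|---|---|---|
| VDS+SU vs SOL+SU | 1 - 0.579 = 0.421 | 0.058 | 0.18 |
| VDS+SU vs SU | 1 - 0.419 = 0.581 | 0.054 | 0.16 |
| SOL+SU vs SU | 1 - 0.343 = 0.657 | 0.0002 | 0.0006 |

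The pattern is the same: a very small three-group P, with neither VDS+SU contrast significant at .05, even before adjustment.

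**Precision the added intervals would have.** Half-width = z × sqrt[2p(1 - p)/87], with z = 1.96, or 2.39 for alpha 0.05/3 = 0.0167.

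| Common rate | 95% half-width (points) | Bonferroni half-width (points) |
|---|---|---|
| 20% | 11.9 | 14.5 |
| 30% | 13.6 | 16.6 |
| 50% | 14.9 | 18.1 |

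**The case against.** Four replies carry weight.

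1. **Frequencies are reported.** If shown by arm, a reader can work out any pairwise difference. This is right, so the gap is in the prespecified inference, not in the data.
2. **The Wilcoxon rule may carry over to the rating.** Elsewhere the plan follows Kruskal-Wallis with pairwise Wilcoxon tests and adjusted P values, and one such paragraph comes just before the rating paragraph. But the text describes the "Wilcoxon rank-sum test, which can compare two groups with continuous data that do not meet ANOVA assumptions", and a Hodges-Lehmann shift has no clear meaning on a verbal scale. The extension is arguable for the rating; nothing comparable exists for the yes/no outcome.
3. **Aim 1 concerns symptoms.** Wanting another therapy is not a symptom. That is fair, and it makes Aim 1 a weaker argument for that outcome. The plan still sets out to compare the arms on it.
4. **These are secondary outcomes.** Agreed; this limits the consequence.

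Three stronger readings are tempting but not supported.

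- *A reader might infer that the plan would often declare a vitamin D benefit where none exists.* Suppose 40% of SU, 40% of VDS+SU and 20% of SOL+SU children want another therapy. The three-group chi-square then has noncentrality 87 × 0.12 = 10.4 and is significant in 83% of trials. But VDS+SU truly differs from SOL+SU by 20 points there, so this is power to detect a real difference, not a false-positive rate. It falls to 56% at 40/40/25 and 27% at 40/40/30. Nor does the plan say that a significant test will be credited to vitamin D.
- *A reader might infer that the 'percentile' summary hides the share answering yes.* Under the plan's definition, the value at the second category is the share in the first. The yes share is therefore that value or its complement, depending on category order, and the frequencies give it directly.
- *A reader might infer that satisfaction is being replaced by willingness to switch.* The sentence in 9.5.2 names both items and defines only the second. That is ambiguous and does not establish a substitution.

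**Conclusion.** The point holds for the prespecified inference. As written, a significant result on perceived improvement or on willingness to receive another therapy would not show whether VDS+SU differs from SOL+SU or from SU, and no effect size or precision is planned for either outcome. It is firm for the yes/no outcome and slightly less so for the rating, where the Wilcoxon rule might be stretched to apply.

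The size depends on rates the documents do not give. The worked counts show that the ambiguity can arise at the planned 87 per arm; they do not predict how often it will. The 'percentile' matter is a wording correction. Severity is low, because both outcomes are secondary and the primary conclusion on voiding frequency is untouched.

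**What to change.** In section 9.5.2, keep the three-group tests and add, at each time point analysed, the three pairwise comparisons (VDS+SU vs SU, VDS+SU vs SOL+SU, SOL+SU vs SU) with the Bonferroni adjustment named in 9.5.1:

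- **Willingness to receive another therapy:** n/N (%) per arm, and the pairwise risk difference with 95% CI and adjusted P value.
- **Perceived improvement:** n/N (%) per category and arm, and a pairwise Wilcoxon rank-sum test with adjusted P value. Add one ordinal effect measure, chosen in advance (probability of a better rating or proportional odds ratio), with 95% CI.

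State whether Bonferroni-level intervals will also be shown, so that intervals and adjusted P values are read consistently. In 9.5 and 9.5.2, replace 'percentile' with percentage (n/N per category).

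The cost is a short SAP edit and a few table columns. No new data, visits or participants are needed. The downside is wider intervals if they are adjusted: at a 30% rate and 87 per arm, 16.6 instead of 13.6 points either side.
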